8.8.3 Exploratory biomarkers

CCI

Additional sample collections and analyses may be completed at select study sites by site-specific amendment. All samples collected for such exploratory analyses will be stored at site, a reference laboratory, or at AstraZeneca's facilities and may be used for subsequent research relevant to evaluating response to immunotherapy.

The exploratory biomarker plan is described by sample type below.

CCI

CCI

CCI

Management of biomarker data

The biomarker data will have unknown clinical significance. AstraZeneca will not provide biomarker research results to patients, their family members, any insurance company, an employer, clinical study Investigator, general physician, or any other third party, unless required to do so by law. The patient's samples will not be used for any purpose other than those described in the study protocol.

Individual patients will not be identified in any report or publication resulting from this work. The data and results of this research may be reviewed with collaborators and published, but neither the patient's name nor any other personal identifiers will appear in any publication or report.

8.8.4 Storage, re-use and destruction of biomarker samples

Samples will be stored for a maximum of 15 years from the end of study, after which they will be destroyed. Summaries and analyses for exploratory biomarkers will be documented in a separate analysis plan and will be reported outside the CSR in a separate report. The results of this biomarker research may be pooled with biomarker data from other studies involving durvalumab or tremelimumab to generate hypotheses to be tested in future research.

8.8.5 Labeling and shipment of biological samples

The PI will ensure that samples are labeled and shipped in accordance with the Laboratory Manual and the Biological Substance, Category B, Regulations (materials containing or suspected to contain infectious substances that do not meet Category A criteria); see [Appendix C](#) "IATA [International Airline Transportation Association] 6.2 Guidance Document."

Any samples identified as Infectious Category A materials will not be shipped, and no further samples will be taken from the involved patients unless agreed upon with AstraZeneca and appropriate labeling, shipment, and containment provisions are approved.

8.8.6 Chain of custody of biological samples

A full chain of custody will be maintained for all samples throughout their life cycle.

The PI at each center will keep full traceability of collected biological samples from the patients while in storage at the center until shipment or disposal (where appropriate) and will keep documentation of receipt of sample shipments.

The sample receiver will keep full traceability of the samples while in storage and during use until used or disposed of or until further shipment and will keep documentation of receipt of arrival.

AstraZeneca will keep oversight of the following: life cycle through internal procedures, monitoring of study sites, auditing and process checks, and contractual requirements of external laboratory providers.

Samples retained for further use will be registered in the AstraZeneca-assigned Biobank and will be registered with the AstraZeneca Biobank Team during the entire life cycle.

8.8.7 Withdrawal of informed consent for donated biological samples

If a patient or his/her legal representative withdraws consent to the use of donated biological samples, the samples will be disposed of or destroyed and the action documented. If samples have already been analyzed, AstraZeneca is not obliged to destroy the results of this research.

The PI will:

- Ensure that AstraZeneca is immediately notified of the patients' withdrawal of informed consent to the use of donated samples.
- Ensure that biological samples from that patient, if stored at the study site, are immediately identified, disposed of or destroyed and the action documented.
- Ensure that the organization(s) holding the samples is/are immediately informed about the withdrawn consent and that samples are disposed of or destroyed, the action is documented, and the signed document is returned to the study site.
- Ensure that the patient and AstraZeneca are informed about the sample disposal.

8.9 Effect of immune checkpoint inhibition in response to routine immunizations

Samples for vaccine titers will be omitted in the smallest patients to ensure that appropriate blood volume limits are adhered to (see Section 8; Volume of blood and prioritization of laboratory sampling).

Blood samples for vaccine antibody titer measurement will be taken during the dose-expansion phase only (Table 2). ^{CCI}

CCI

9. STATISTICAL CONSIDERATIONS

The primary aim of the dose-finding phase of the study is to determine the adult equivalent exposure/MTD and safety profile of durvalumab and durvalumab in combination with tremelimumab, in children and young adults using a q4w dosing schedule.

The primary aim of the dose-expansion phase is to determine the preliminary antitumor activity of those recommended doses.

Analyses will be performed by AstraZeneca or its representatives.

A statistical analysis plan (SAP) containing details of all planned statistical analyses will be produced prior to first-patient-in and the mock output shells within 3 months of the first patient enrolled.

9.1 Statistical hypotheses

There is no formal statistical testing for the dose-finding phase of the study.

The dose-expansion phase of the study will formally test the following hypothesis:

- H0: ORR \leq 10%
- H1: ORR $>$ 10%.

The test will be performed for the SARCOMA cohort and it will be done at the 1-sided 5% level. No formal statistical testing will be performed for the STO cohort.

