9.2 Sample size determination

Dose-finding phase

The final sample size in the dose-finding phase will depend on the number of DLTs and on the number of DLs to be explored. In addition, any patients not evaluable (NE) will be replaced in order to have the required number of patients evaluable at each DL. A minimum of 12 patients is anticipated to be dosed, to enable exploration of 1 DL in both patients weighing 35 kg and greater, and patients weighing under 35 kg. If all 3 DLs are used at both weight-based arms, then 36 evaluable patients would be necessary to complete the dose-finding phase. If approximately 20% of patients need to be replaced due to non-evaluability, then a maximum of 45 patients will be enrolled on the dose-finding cohorts.

Dose-expansion phase

For the dose-expansion phase, the SARCOMA cohort mentioned in Section 4.1.4 will follow a Simon 2-stage optimal design. An ORR $\leq 10\%$ will not be considered clinically meaningful.

In the SARCOMA cohort, the Simon 2-stage design will have a type I error rate set at 0.1 (1-sided) and power of at least 85%. Based on the assumption that the ORR for the null hypothesis is 10% and the true ORR for the SARCOMA cohort is 30%, then the SARCOMA cohort will require a total of 26 evaluable patients (with the requirement that $\geq 40\%$ of the patients enrolled must have soft-tissue sarcomas), with 11 evaluable patients required in the first stage. If fewer than 2 responses are observed in the first 11 evaluable patients, then the cohort will be closed for lack of benefit. If 2 or more responses are observed out of the first 11 evaluable patients, then an additional 15 evaluable patients will be enrolled, for a total of 26 evaluable patients.

For a cohort that enrolls the maximum total of evaluable patients for that particular cohort (26 patients in the SARCOMA cohort), if fewer than 5 responses are observed out of the maximum total of evaluable patients, then no further investigation of this cohort will be done; if 5 or more responses are observed out of the maximum total of evaluable patients, then the null hypothesis will be rejected for this cohort and further investigation will be warranted.

The STO cohort is planned to recruit 10 evaluable patients. This sample size is based on practical, rather than formal considerations, as no formal hypothesis testing is planned for this cohort.

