1.3 Number of patients

Dose-finding phase

The final sample size in the dose-finding phase will depend on the number of DLTs and on the number of dose levels to be explored. In addition, any patients not evaluable (NE) will be replaced in order to have the required number of patients evaluable at each dose level. A minimum of 12 patients is anticipated to be dosed, to enable exploration of 1 dose level in both patients weighing 35 kg and greater, and patients weighing under 35 kg. If all 3 dose levels are used at both weight-based arms, then 36 evaluable patients would be necessary to complete the dose-finding phase. If approximately 20% of patients need to be replaced due to non-evaluability, then a maximum of 45 patients will be enrolled on the dose-finding cohorts.

Dose-expansion phase

For the dose-expansion phase, the SARCOMA cohort will follow a Simon 2-stage optimal design. An ORR $\leq 10\%$ will not be considered clinically meaningful.

In the SARCOMA cohort, the Simon 2-stage design will have a type I error rate set at 0.1 (1-sided) and power of at least 85%. Based on the assumption that the ORR for the null hypothesis is 10% and the true ORR for the SARCOMA cohort is 30%, then the SARCOMA cohort will require a total of 26 evaluable patients (with the requirement that $\geq 40\%$ of the patients enrolled must have soft-tissue sarcomas), with 11 evaluable patients required in the first stage. If fewer than 2 confirmed responses are observed in the first 11 evaluable patients, then the cohort will be closed for lack of benefit. If 2 or more responses are observed out of the first 11 evaluable patients, then an additional 15 evaluable patients will be enrolled, for a total of 26 evaluable patients.

For a cohort that enrolls the maximum evaluable patients for that particular cohort (26 in the SARCOMA cohort), if fewer than 5 responses are observed out of the maximum total of evaluable patients, then no further investigation of that cohort will be done; if 5 or more responses are observed out of the maximum total of evaluable patients, then the null hypothesis will be rejected for this cohort and further investigation will be warranted.

The STO cohort is planned to recruit 10 evaluable patients. This sample size is based on practical, rather than formal considerations, as no formal hypothesis testing is planned for this cohort.

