4 ANALYSIS METHODS

4.1 General principles

The primary analysis cut off will be defined at approximately 6 months after enrollment of the last patient. At this point, data analysis will be performed, and the CSR will be written. After this, patients still in the study will continue to be followed and a CSR addendum will be issued for OS and safety data collection.

For PK and other biomarkers, the sample bioanalysis will be performed by AstraZeneca or a contracted laboratory. PK parameters will be derived by Labcorp. The merging of PK concentration data with actual elapsed time from dose for PK sampling times will be performed by IQVIA Programming. The PK summaries and data listings will be the responsibility of IQVIA Biostatistics.

Statistical summaries and analyses of non-PK data will be performed by IQVIA under the direction of the Biostatistics Group, AstraZeneca using SAS® version 9.4 or higher and, where appropriate, additional validated software.

There is no formal statistical testing for the dose-finding phase of the study.

The dose-expansion phase of the study will formally test the following hypothesis:

- H_0 : ORR \leq 10%
- H_1 : ORR $>$ 10%.

The test will be done at the 1-sided 5% level and it will be performed for the SARCOMA cohort.

No formal statistical testing will be performed for the STO cohort.

For the dose-finding phase, and dose-expansion phase where relevant, dose levels will be labelled in summary tables as:

- durvalumab xx mg/kg + tremelimumab xx mg/kg

with xx depending on the dose levels used.

For the dose-expansion phase, cohorts will be labelled in summary tables as:

- SARCOMA
- STO

Total columns will be included for the dose-finding and dose-expansion phases separately for outputs where a total column is required.

Visits will be present as cycle and day (e.g. Cycle 1 Day 1). Study day will be calculated as follows:

Days prior to first dose: Study day = date – first dose date

Days on or after first dose: Study day = date – first dose date + 1

First dose refers to either durvalumab or tremelimumab, whichever was administered first. Dates of progression will not be imputed.

The end of study is defined as the last expected visit/contact of the last patient undergoing the study. A patient is considered to have completed the study when he/she has completed his/her last scheduled visit shown in the schedule of activities (CSP section 1.1).

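### The SARCOMA response test is stated at 1-sided 5%, but the Simon rule that rejects at 5 of 26 is a 1-sided 10% design with exact type I error 8.65%

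*Protocol*

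**What the plan says.** The level of the test is given in two ways.

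- **1-sided 5%.** Protocol 9.1 states of H0: ORR at most 10%: "The test will be performed for the SARCOMA cohort and it will be done at the 1-sided 5% level". The Synopsis (Statistical methods) has the same sentence, and SAP 4.1 says "The test will be done at the 1-sided 5% level and it will be performed for the SARCOMA cohort".
- **1-sided 10%.** Protocol 9.2 says "the Simon 2-stage design will have a type I error rate set at 0.1 (1-sided) and power of at least 85" percent. SAP 1.3 repeats that "the Simon 2-stage design will have a type I error rate set at 0.1". Both then give the same final rule: "if 5 or more responses are observed out of the maximum total of evaluable patients, then the null hypothesis will be rejected".

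The ORR interval is a 2-sided 90% interval (Protocol 9.5.1 and 9.5.1.1; SAP 4.2.2.1), by the Mid-P method if the cohort is expanded. SAP 4.2.2.1 ties its limits to a one-sided Mid-p value of 0.05. SAP 6, which lists departures from the protocol, does not mention the two levels. Dose-finding and the STO cohort have no formal test, so this is the only one in the study.

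**The concern.** One cohort, one null hypothesis and one test carry two significance levels. Section 9.2 cannot be read as planning background only, because it says when the null hypothesis is rejected. If the 5-of-26 rule has a type I error above 5%, then a result of exactly 5/26 rejects H0 under 9.2 and fails to reject it under 9.1.

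At stake is the conclusion on the primary endpoint at the design's own success threshold. If 5/26 occurred, the level would have to be chosen after the data were seen. The report could also declare H0 rejected next to an interval that contains the null value. Whatever the count, describing the rule as a 5% test would understate its false-positive rate.

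**Working it through.** **Inputs (Protocol 9.2, matched in SAP 1.3)**

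- p0 = 0.10 and p1 = 0.30: "the ORR for the null hypothesis is 10% and the true ORR for the SARCOMA cohort is 30" percent.
- n1 = 11: "with 11 evaluable patients required in the first stage".
- Stage 1 stop at 1 or fewer responses: "If fewer than 2 responses are observed in the first 11 evaluable patients, then the cohort will be closed for lack of benefit".
- n = 26, so the second stage has 15 patients. Reject H0 at 5 or more.

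**Formula.** With X1 ~ Bin(11, p), X2 ~ Bin(15, p) and final cut-off c:

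P(reject) = sum over x1 = 2 to 11 of P(X1 = x1) × P(X2 ≥ c − x1)

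**1. The stated rule, c = 5**

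| x1 | p = 0.10 | p = 0.30 |
|---|---|---|
| 2 | 0.2131 × 0.1841 = 0.0392 | 0.1998 × 0.8732 = 0.1744 |
| 3 | 0.0710 × 0.4510 = 0.0320 | 0.2568 × 0.9647 = 0.2478 |
| 4 | 0.0158 × 0.7941 = 0.0125 | 0.2201 × 0.9953 = 0.2191 |
| 5 or more | 0.0028 × 1 = 0.0028 | 0.2103 × 1 = 0.2103 |
| Sum | **0.0865** | **0.8516** |

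This meets a type I error of 0.10 and power of 85%. An exhaustive search at those targets also returns 1/11, 4/26 as the optimal design (expected size under H0 15.5). The plan's design therefore reproduces at 10%. Its exact type I error is 0.0865/0.05 = 1.73 times the 5% stated in 9.1.

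**2. A 5% test on the same patients.** The smallest cut-off that meets 5% is c = 6. At p = 0.10 the terms for x1 = 2, 3, 4, 5 and 6 or more are 0.0118 + 0.0131 + 0.0071 + 0.0020 + 0.0003 = **0.0343**. Power at p = 0.30 is **0.787**. A 5% level, 85% power and the 11/26 design cannot all hold.

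**3. What happens at exactly 5/26 (19.2%).** The documents do not name the statistic for the 5% test, so four versions were checked against p0 = 0.10.

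| Method | 1-sided p at 5/26 | Lower 90% limit at 5/26 | 1-sided p at 6/26 |
|---|---|---|---|
| Two-stage exact | 0.0865 | 8.5% | 0.0343 |
| Two-stage mid-p | (0.0865 + 0.0343)/2 = 0.0604 | 9.5% | 0.0226 |
| Single-stage exact | 0.1118 | 7.9% | 0.0399 |
| Single-stage mid-p | (0.1118 + 0.0399)/2 = 0.0758 | 8.9% | 0.0259 |

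At 5/26 every p-value exceeds 0.05 and every lower limit is below 10%. The full 90% Mid-P interval is 8.9% to 34.5% (binomial) or 9.5% to 38.5% (two-stage sample space). At 6/26 every version rejects.

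**4. How often it arises.** P(exactly 5/26) = P(reject at c = 5) − P(reject at c = 6). This is 5.2% at p = 0.10 (0.0865 − 0.0343), 14.1% at p = 0.20 and 6.5% at p = 0.30 (0.8516 − 0.7867).

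**The case against.** The case for leaving this as a minor point has four parts.

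- **The design is sound and only one outcome is affected.** The Simon calculation is correct at its stated 10%. With 4 or fewer responses neither rule rejects, and with 6 or more both do. If the cohort closes at stage 1, the final test never arises. All of this stands: the fault is a contradiction between sections, not an error in the sample-size calculation.
- **The only operational rule is 5 of 26.** The 5% sentence gives no statistic or cut-off, so the non-rejection at 5/26 has to be inferred. That is fair, but the inference does not depend on the choice: the four versions run from 0.060 to 0.112.
- **The 90% interval is a general reporting convention.** Protocol 9.5.1 applies it by default, and the disease control rate, which has no test, uses it too. No section says the ORR interval decides H0. The interval therefore does not show that 5% was intended. It would still appear beside a rejection while containing 10%.
- **This is an early-phase cohort seeking preliminary activity, with committee decisions on expansion and closure.** That lowers the consequences. But the documents chose to make this a formal test of the primary endpoint, and its level should be unambiguous before the data are analysed.

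**Conclusion.** The plan is wrong as written. The 1-sided 5% level in the Synopsis, Protocol 9.1 and SAP 4.1 does not describe the rejection rule in Protocol 9.2 and SAP 1.3, whose exact type I error is 8.65%. The conclusion conflicts at exactly 5/26 and nowhere else, but the stated false-positive rate is too low for the rule whatever the count.

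These figures assume exactly 11 and then 15 evaluable patients, independent responses with a common response probability, and adherence to the stage 1 stopping rule. Which level was intended cannot be settled from the documents. The sample size and cut-off fit 10%; the confidence level of the interval corresponds to 5%.

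**What to change.** Use one level throughout.

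- **Keep the design (simplest).** In the Synopsis, Protocol 9.1 and SAP 4.1, replace the 5% level with 1-sided 10% (exact 8.7%), and state that H0 is rejected by the Simon rule, 5 or more of 26. Sample size, stage 1 rule, cut-off and power stay the same. To give an interval that agrees with the test, add an 80% 2-sided Mid-P interval beside the 90% one. Its lower limit is 10.8% (binomial) or 11.6% (two-stage) at 5/26, and 8.0% or 9.1% at 4/26, so it falls on the correct side of 10% both times. The method must be named: a Clopper-Pearson 80% interval has a lower limit of 9.7% at 5/26 and the mismatch would return. The extra interval is helpful but not essential to remove the contradiction.
- **If 5% is intended with 26 patients.** Change the cut-off to 6 or more of 26 and restate power as about 79%.
- **If 5% and 85% power are both intended.** The Simon optimal design becomes 11 then 35 patients, stopping at 1 or fewer of 11 and rejecting at 7 or more (type I error 0.0422, power 0.851). The minimax design is 18 then 27 patients, stopping at 2 or fewer of 18 and rejecting at 6 or more (0.0444, 0.8505).

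The first option costs wording in three places and, if adopted, one extra interval. It needs no extra patients; the price is a less favourable stated error rate. The third option needs up to 9 more evaluable patients (35 − 26), or a larger first stage with 1 more in total (27 − 26).

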9.2 Sample size determination

Dose-finding phase

The final sample size in the dose-finding phase will depend on the number of DLTs and on the number of DLs to be explored. In addition, any patients not evaluable (NE) will be replaced in order to have the required number of patients evaluable at each DL. A minimum of 12 patients is anticipated to be dosed, to enable exploration of 1 DL in both patients weighing 35 kg and greater, and patients weighing under 35 kg. If all 3 DLs are used at both weight-based arms, then 36 evaluable patients would be necessary to complete the dose-finding phase. If approximately 20% of patients need to be replaced due to non-evaluability, then a maximum of 45 patients will be enrolled on the dose-finding cohorts.

Dose-expansion phase

For the dose-expansion phase, the SARCOMA cohort mentioned in Section 4.1.4 will follow a Simon 2-stage optimal design. An ORR $\leq 10\%$ will not be considered clinically meaningful.

In the SARCOMA cohort, the Simon 2-stage design will have a type I error rate set at 0.1 (1-sided) and power of at least 85%. Based on the assumption that the ORR for the null hypothesis is 10% and the true ORR for the SARCOMA cohort is 30%, then the SARCOMA cohort will require a total of 26 evaluable patients (with the requirement that $\geq 40\%$ of the patients enrolled must have soft-tissue sarcomas), with 11 evaluable patients required in the first stage. If fewer than 2 responses are observed in the first 11 evaluable patients, then the cohort will be closed for lack of benefit. If 2 or more responses are observed out of the first 11 evaluable patients, then an additional 15 evaluable patients will be enrolled, for a total of 26 evaluable patients.

For a cohort that enrolls the maximum total of evaluable patients for that particular cohort (26 patients in the SARCOMA cohort), if fewer than 5 responses are observed out of the maximum total of evaluable patients, then no further investigation of this cohort will be done; if 5 or more responses are observed out of the maximum total of evaluable patients, then the null hypothesis will be rejected for this cohort and further investigation will be warranted.

The STO cohort is planned to recruit 10 evaluable patients. This sample size is based on practical, rather than formal considerations, as no formal hypothesis testing is planned for this cohort.

With the above considerations, the sample size for evaluable patients in the dose-expansion phase is expected to range from 21 to 36. Assuming that about 20% of patients may not be evaluable for ORR, the total number of patients dosed in the dose-expansion phase may range from approximately 25 to 43.

9.3 Populations for analyses

Definitions of the analysis sets for each outcome variable are provided in [Table 22](#).

Table 22 Summary of outcome variables and analysis populations

Outcome variable	Populations
Efficacy Data	
ORR (primary for dose-expansion phase)	Evaluable for response analysis set (Sensitivity analysis on FAS)
PFS, OS, BoR, APF12, APF18, OS12, OS24	FAS (ITT population)
DoR	Evaluable for response analysis set (restricted to responders only)
DCR	Evaluable for response analysis set (Sensitivity analysis on FAS)
Demography	FAS (ITT population)
PK data	PK analysis set
Safety Data	
Exposure	SAS
AEs	SAS
Laboratory measurements	SAS
Vital Signs	SAS
DLTs (primary for dose-finding phase)	DLT evaluable analysis set

AE Adverse event; APF12 / APF18 Proportion of patients alive and progression-free at 12 / 18 months from first dose of IP; BoR Best objective response; DCR Disease control rate; DLT Dose-limiting toxicity; DoR Duration of response; FAS Full analysis set; ITT Intention-to-treat; OS Overall survival; OS12 / OS24 Proportion of patients alive at 12 / 24 months from first dose of IP; PFS Progression-free survival; PK Pharmacokinetics; SAS Safety analysis set.

